7.2.2 Documentation of AEs

All AEs are to be evaluated for duration, intensity, and relationship to (associated with) the trial treatment or due to other causes including underlying disease.

All AEs (problems, complaints, signs, and symptoms and clinically relevant laboratory abnormalities), both those observed by trial site personnel and those spontaneously reported by the trial subjects, must be recorded on the AE page in the eCRF, as well as in the subject's medical record using standard medical terminology **regardless of causality**. If an AE occurred after signing the ICF, but the subject withdraws from the trial before receiving any trial treatment, the AE should be recorded in the eCRF.

Each event should be recorded as a single diagnosis. Accompanying signs (including abnormal laboratory values, physical examination findings, pulmonary or cardiovascular function tests) or symptoms should not be recorded as additional AEs. However, if the diagnosis is unknown or uncertain, signs and symptoms must be recorded. As soon as the diagnosis causing the signs and symptoms is known, the event terms will be adjusted to the final diagnosis.

For each AE, a minimum required information should be reported, which includes:

- The type of AE,
- An estimate of its severity (using NCI-CTCAE version 5.0, see [Appendix C](#)),
- Date and time of occurrence,
- Date of resolution,
- Actions required,
- An assessment of its causal relationship to trial medication (using the WHO system for standardized case causality assessment, provided separately in the investigator File).

AEs resulting from disease relapse/ progression themselves are not considered to be an AE. Likewise, any medical condition that is present at the Screening Visit will be considered as baseline and will not be reported as an AE but as medical history. However, if the condition changes at any time during the trial, it will be recorded as an AE. Investigators should ensure that the event term recorded captures the change in the condition (e.g., “worsening of...”).

7.2.2.1 Severity of AEs

Each AE is to be classified and graded according to CTCAE v5.0 criteria (see [Appendix C](#)). Dates of onset and resolution, including dates at which the grade of an AE changes, are to be recorded in the subject file.

If no CTCAE grading is available, the severity of an AE is to be graded as follows:

- **Mild (Grade 1):** the event causes discomfort without disruption of normal daily activities.
- **Moderate (Grade 2):** the event causes discomfort that affects normal daily activities.
- **Severe (Grade 3):** the event makes the subject unable to perform normal daily activities or significantly affects his/her clinical status.
- **Life-threatening (Grade 4):** the subject was at risk of death at the time of the event or the event caused death.
- **Death (Grade 5):** death related to an AE.

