2.2 Endpoints

2.2.1 Primary Endpoints

The primary endpoints are:

- Type and number of AEs according to National Cancer Institute (NCI) – Common Terminology Criteria for Adverse Events (CTCAE) criteria v5.0, and additional safety parameters of CyPep-1 as monotherapy and in combination with pembrolizumab.
- Dose limiting toxicities (DLTs) and the maximum tolerated dose (MTD) for determination of RP2D of CyPep-1 as monotherapy and treatment-limiting toxicities (TLTs) of CyPep-1 in combination with pembrolizumab.

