8.1.3 Adverse Events

Analyses of AEs will be based on the SAF set. AEs will be coded according to CTCAE v5.0 (for severity) and the Medical Dictionary for Regulatory Activities (MedDRA).

The total number/incidence of AEs will be summarized, including the number of subjects with at least one AE and the number of unique AEs per cohort and overall. The number of AEs per

severity (CTCAE) and relation to trial drug will also be included and summarized per cohort and overall. Additionally, listings of AEs leading to treatment discontinuation, resulting in death, and according to maximum severity will be tabulated. The incidence DLT/TLTs will also be evaluated for each dose level, and for all subjects combined. SAEs will be summarized in a similar manner.

The number of subjects and the number of AEs will be tabulated by MedDRA system organ class and preferred term. AEs will also be tabulated versus worst severity and worst relationship to treatment. In this table, subjects with AEs will be identified by their subject number.

Vital signs and body weight, 12-lead ECG parameters, laboratory data (hematology, biochemistry, coagulation, urinalysis) will be summarized using descriptive statistics. Shift tables showing changes from baseline will be generated where appropriate.

Pre-treatment events occurring between first assessment at screening and first dose of CyPep-1 will be summarized separately.

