Appendix C: Common Terminology Criteria for Adverse Events (CTCAE) version 5.0

CTCAE term (AE description) and grade: The descriptions and grading scales found in the revised NCI-CTCAE version 5.0 will be utilized for AE reporting. All appropriate treatment areas should have access to a copy of the CTCAE version 5.0. A copy of the CTCAE version 5.0 can be downloaded from the CTEP web site: http://ctep.cancer.gov/protocolDevelopment/electronic_applications/ctc.htm

Quick Reference

The NCI-CTCAE is a descriptive terminology, which can be utilized for Adverse Event (AE) reporting. A grading (severity) scale is provided for each AE term.

Components and Organization

System Organ Class (SOC), the highest level of the Medical Dictionary for Regulatory Activities (MedDRA) hierarchy, is identified by anatomical or physiological system, etiology, or purpose (e.g. SOC Investigations for laboratory test results). CTCAE terms are grouped by MedDRA Primary SOCs. Within each SOC, AEs are listed and accompanied by descriptions of severity (Grade).

CTCAE Terms

An AE is any unfavorable and unintended sign (including an abnormal laboratory finding), symptom, or disease temporally associated with the use of a medical treatment or procedure that may or may not be considered related to the medical treatment or procedure. An AE is a term that is a unique representation of a specific event used for medical documentation and scientific analyses. Each CTCAE v 5.0 term is a MedDRA LLT (Lowest Level Term).

Definitions

A brief definition is provided to clarify the meaning of each AE term.

Grades

Grade refers to the severity of the AE. The CTCAE displays Grades 1 through 5 with unique clinical descriptions of severity for each AE based on this general guideline:

- Grade 1 Mild: asymptomatic or mild symptoms; clinical or diagnostic observations only; intervention not indicated.
- Grade 2 Moderate: minimal, local or non-invasive intervention indicated; limiting age-appropriate instrumental activities of daily living.
- Grade 3 Severe or medically significant but not immediately life-threatening: hospitalization or prolongation of hospitalization indicated; disabling; limiting self-care ADL.
- Grade 4 Life-threatening consequences: urgent intervention indicated.
- Grade 5 Death: related to AE.

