Subjects with PTs of “Cancer Pain” and “Tumour Pain” will be pooled for outputs under PT of “Cancer Pain”. Similar pooling will be applied for inconsistently reported injection site reactions; list of applicable AEs will be provided by Sponsor/Data Management/Medical Monitor and reviewed at the Data Review Meeting before the database lock. In listings, such AEs will be flagged as pooled for tables but presented with the PT reported on eCRF (i.e., no pooling will be applied for listings).

For summaries of TEAEs by SOC and PT, a subject will be counted once within an SOC, even if the subject experienced more than one TEAE within a specific SOC (likewise for PT). For summaries of TEAEs by CTCAE v5.0 grade, a subject will be counted at most once at each severity grade within a SOC and/or PT. A missing severity will be assumed to be Grade 3. A missing relationship will be assumed to be likely related unless the subject was never treated with the specific therapy. Summaries of TESAEs by SOC and PT will be handled in a similar manner as TEAEs. A missing seriousness assessment will be assumed serious.

Summaries of adverse events by SOC and PT will include the following types:

Statistical Analysis Plan

SMS-0571/CyPep-1
V3.0 Final
04-Jun-2024

1. TEAEs,
2. TEAEs by CTCAE grade,
3. TEAEs related to any study treatment (CyPep-1 or pembrolizumab),
4. TEAEs related to CyPep-1,
5. TESAEs,
6. TESAEs by CTCAE grade,
7. TESAEs related to any study treatment (CyPep-1 or pembrolizumab),
8. TESAEs related to CyPep-1,
9. CTCAE Grade 3 or higher TEAEs,
10. CTCAE Grade 3 or higher TEAEs related to any study treatment (CyPep-1 or pembrolizumab),
11. CTCAE Grade 3 or higher TEAEs related to CyPep-1,
12. TEAEs related to CyPep-1 by CTCAE grade,
13. TEAEs leading to CyPep-1 discontinuation,
14. TEAEs leading to CyPep-1 discontinuation by CTCAE grade,
15. TEAEs leading to CyPep-1 discontinuation related to CyPep-1,
16. TEAEs leading to study discontinuation,
17. TEAEs leading to study discontinuation by CTCAE grade,
18. TEAEs leading to study discontinuation related to any study treatment (CyPep-1 or pembrolizumab)
19. TEAEs leading to study discontinuation related to CyPep-1,
20. Dose limiting toxicities,
21. Treatment limiting toxicities (TLTs),
22. Fatal TEAEs by relatedness to any study treatment,
23. Pre-treatment AEs.

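### The fallback severity scale lets a fatal adverse event be graded 4 as well as 5, so the Grade 4/5 split in the AE tables can be misstated (minor)

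*Protocol*

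**What the plan says.** Protocol 7.2.2.1 requires CTCAE v5.0 grading and then adds a fallback: "If no CTCAE grading is available, the severity of an AE is to be graded as follows". The two top grades of that fallback, beside the general guideline in Appendix C, read:

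| Grade | Fallback scale (7.2.2.1) | Appendix C |
|---|---|---|
| 4 | "the subject was at risk of death at the time of the event or the event caused death" | "Grade 4 Life-threatening consequences: urgent intervention indicated" |
| 5 | "death related to an AE" | "Grade 5 Death: related to AE" |

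The grades feed the safety tables. Protocol 8.1.3 states that "AEs will also be tabulated versus worst severity and worst relationship to treatment". SAP 11.1.3 plans several tables of TEAEs and serious TEAEs by CTCAE grade, in which "a subject will be counted at most once at each severity grade within a SOC and/or PT". It also plans overview rows, a table and a listing for fatal TEAEs, without saying whether an event counts as fatal by its outcome or by its grade. SAP 11.2 summarises deaths separately, by primary cause, for the whole safety set.

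**The concern.** A severity scale needs grades that exclude one another. Here two investigators who both follow the protocol to the letter can record the same fatal event differently, one as Grade 4 and the other as Grade 5. Nothing in the SAP repairs this. Its only severity imputation sets a missing grade to 3, with no exception for a fatal event, and no rule reconciles grade with outcome.

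At stake is whether the report agrees with itself on fatal events. If fatal TEAEs are picked by outcome, the fatal rows and the by-grade tables of the same report could differ. If they are picked as Grade 5, the fatal rows would miss an event coded 4.

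**Working it through.** The plan states no figure that can be reproduced here. The check is a comparison of definitions, followed by a trace of the grade into each place that uses it.

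**Do the fallback grades overlap?** Take an event on the fallback scale that caused death. It satisfies the second alternative of Grade 4, and it satisfies Grade 5. One might read Grade 4 as applying to the causing event and Grade 5 to the death as a separate record. However, Protocol 7.2.2 asks for each event to be recorded as a single diagnosis, so one record has to carry one grade. The overlap stands.

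**Does the rest of the protocol separate the two?** Yes. Appendix C has no death in Grade 4. The SAE definition in Protocol 7.1.5 lists death and life-threatening as different criteria, and its life-threatening item uses the at-risk wording without the death clause.

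**What changes when one fatal event is coded 4 instead of 5?**

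- By-grade tables: the Grade 4 count rises by up to one subject and the Grade 5 count falls by up to one.
- Rows and tables for Grade 3 or higher: no change, because 4 and 5 both qualify.
- Fatal TEAE rows, table and listing: no change if selected by outcome, one too few if selected as Grade 5. The SAP does not say which.
- Deaths table (SAP 11.2): no change, because it rests on cause of death and not on AE grade.
- DLT status (Protocol 3.1.2): no change, because the threshold is Grade 3 or higher.
- TLT status (Protocol 3.1.2): TLTs are graded by CTCAE v5.0, so on its face the fallback does not govern them. Even if it did, a related fatal non-haematologic event coded 4 in Cycle 1 meets items 1 and 3. A fatal haematologic event coded 4 might fall short of the 7-day condition in item 2. In practice it would be caught by item 7, which covers treatment-related toxicity that ends treatment in Cycle 1.

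**Size per event.** The shift in the Grade 5 rate from one miscoded subject is 1/n, with n the planned number of subjects:

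- Arm A expanded, n = 18: 1/18 = 5.6 percentage points.
- Arm B, n = 15: 1/15 = 6.7 points.
- Arm A not expanded, or Arm C in total, n = 9: 1/9 = 11.1 points.

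These are shifts given that one such event occurs. They are not an expected bias.

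**The case against.** The best case against the point is that it hardly ever bites and that fatal events are visible elsewhere. For an error to arise, an AE-related death must occur, the event must have no CTCAE grading, and the investigator must choose the life-threatening grade although the next line of the scale is labelled as death. The documents give no likelihood for that chain. Outcome is collected separately from severity (Protocol 7.2.1, SAP 11.1). Protocol 8.1.3 lists AEs resulting in death apart from AEs by maximum severity, which points to selection by outcome. The planned tables are described in a separate document that is not available here and may settle the derivation. All of this stands, and it is why the point is minor. It does not remove the contradiction in 7.2.2.1 or the SAP's silence on how fatal TEAEs are selected.

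Three stronger readings are tempting, and the documents support none of them:

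- That deaths would disappear from the report. The deaths table does not depend on AE grade.
- That a fatal toxicity could escape the TLT rule by missing the Grade 5 item. Other TLT items catch it, as traced above.
- That grade is itself the primary endpoint. Protocol 2.2.1 names the type and number of AEs under CTCAE v5.0. Recording 4 instead of 5 changes neither, and grade enters through the CTCAE reference and the tables.

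**Conclusion.** The point holds as a drafting error with a narrow effect. The fallback Grade 4 definition overlaps with Grade 5 and contradicts Appendix C. A fatal event graded on that scale can therefore sit in the wrong row of the by-grade AE tables and, if fatal events are programmed by grade, be missing from the fatal TEAE rows. The range of 5.6 to 11.1 points assumes planned arm sizes and exactly one such event in the arm. How many events will lack a CTCAE grading is not stated. The reason to act is that the correction is nearly free, not that the error is expected to be frequent.

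**What to change.** 1. In Protocol 7.2.2.1, delete from fallback Grade 4 the alternative under which the event caused death, so that the scale agrees with Appendix C and a fatal event has one grade.
2. In SAP 11.1.3, state that a fatal TEAE is one with a fatal outcome or Grade 5.
3. Before database lock, query every AE where a fatal outcome and Grade 5 disagree in either direction, including fatal events with a missing grade, which would otherwise be imputed as Grade 3.

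The first change is one phrase, but it needs an amendment under Protocol 10.6, and it would not correct grades already recorded: Phase I ended in August 2021 and a mid-study analysis was run in summer 2023. The second and third changes cost one sentence and one edit check. They cover the existing data, are worth making even if an amendment is judged impractical this late, and fit the Data Review Meeting already planned before hard lock (SAP 7.1).

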7.2.2.2 Relationship to Trial Treatment

The investigator should use medical judgment to determine whether there is a reasonable causal relationship, including all relevant factors such as temporal course and latency, pattern of the reaction, known pharmacological properties of the product, and alternative explanations (e.g., other drugs, medical history, and concomitant diseases). The expression “reasonable causal relationship” means to convey in general that there is evidence or argument to suggest a causal relationship. The relationship of an AE to trial medication will be recorded on the eCRF and defined as follows:

- **Not Related:** An AE that does not follow a reasonable temporal sequence related to IMP and / or pembrolizumab and is likely to have been produced by the patient’s clinical state, other modes of therapy or other known etiology.
- **Unlikely Related:** An AE that follows such a temporal sequence from administration of the study medication (IMP and / or pembrolizumab) that a relationship is not likely, and is likely

to be due to a cause such as (known characteristics of) the patient's clinical state or other treatment.

- **Possibly Related:** AE that has a reasonable possibility that the event may have been caused by IMP and / or pembrolizumab. The AE has a timely relationship to the IMP and / or pembrolizumab; however, the pattern of response is untypical, and an alternative cause seems more likely or there is significant uncertainty about the cause of the event.
- **Probably Related:** An AE that has a reasonable possibility that the event is likely to have been caused by IMP and / or pembrolizumab. The AE has a timely relationship and follows a known pattern of response, but a potential alternative cause may be present.
- **Definitively Related:** There is a reasonable possibility that the event may have been caused by IMP and / or pembrolizumab. A certain event has a strong temporal relationship and an alternative cause is unlikely.

Ultimately, at the time of data analysis, the relationship to the AE will be categorized as either “**unrelated**” (including, unlikely or not related) or “**related**” (including definitely, probably or possibly related).

7.2.3 Reporting of SAEs

Information on SAEs will be collected from the time of ICF signature until the FU visit (or until EoT, if it occurs more than 30 days after the last CyPep-1 or pembrolizumab administration). After the FU visit (or EoT visit, if it occurs more than 30 days after the last CyPep-1 or pembrolizumab administration), only ongoing AEs or SAEs related to CyPep-1 and / or pembrolizumab administration will be collected.

Specific timing for Arm B is provided in [Section 7.2.1.3](#).

All AEs that meet the criteria for SAE require the completion of a trial specific SAE Form (or Additional Safety Information [ASI] Form), including an assessment of the relationship to the trial drug. This applies to all SAEs, whether or not they were considered to be related to the trial treatment.

The investigator must report all SAEs to [REDACTED] immediately, i.e. within 24 hours (by fax or e-mail) of learning of its occurrence. For this reporting, a SAE Form (provided in the investigator File) needs to be completed in English. The original SAE report form, together with the fax confirmation sheet (if applicable) or e-mail, must be kept at the study site. Follow-up information about a previously reported SAE must also be reported to [REDACTED] within 24 hours of receiving the information. This follow-up data must be provided on an ASI Form or an updated SAE form. The SAE report should provide a detailed description of the AE and should include anonymized copies of hospital records and other relevant documents. Autopsy results, if applicable, should also be sent to [REDACTED] as soon as they become available. Copies of each report will be kept in the investigator File.

All SAEs will need to be followed actively until resolution or stabilization. The above is also applicable to follow-up SAE information.

7.2.4 SUSARs

[REDACTED] on behalf of Cytovation, is required by law to report to the health authorities in a written safety report: 1) all fatal or life-threatening SUSARs within seven (7) calendar days of initial notification; and 2) all other SUSARs within fifteen (15) calendar days of initial notification.

All investigators in the trial will be informed about SUSARs that have occurred [REDACTED] on behalf of Cytovation.

8. STATISTICAL METHODS

8.1 Statistical Analytical Plan

A statistical analysis plan (SAP) will be written in which the details of the statistical methods will be described. The SAP will be finalized before database lock. Any deviations from the originally planned statistical analysis or SAP will be described and justified in the clinical trial report. Changes known at the time of SAP preparation will also be described in the SAP.

A data review meeting will be held before database hard lock. Protocol deviations will be reviewed during the data review meeting. Furthermore, assignment of subjects to the analysis sets will be performed.

Data of subjects who did not meet the entry criteria (screening failures) and data of subjects who received no investigational product (e.g., due to withdrawal) entered in the clinical database will only be listed. Minimal information will include date of ICF signed, demography, screen failure details and eligibility criteria, end of study form, SAEs if applicable. These data will be entered into the eCRF. These data will not be included in the evaluation of any analysis population.

8.1.1 Data Sets to be Analyzed

The analysis population sets are defined as follows:

All Screened Set (SCR): All subjects who were screened for the study and signed informed consent. This analysis set will be used for subject disposition table and for creation of listings.

Safety Analysis Set (SAF): All subjects who received at least one dose of trial drug (CyPep-1 or pembrolizumab in the combination arm). All analyses (except for PK) will be based on this analysis set.

CyPep-1 PK Analysis Set: The first 9 subjects of Phase I, all subjects of Phase IIa Arm C, and the first 12 subjects of Phase IIa Arm D who received at least one dose of CyPep-1, have no clinically important protocol deviations or important events considered affecting PK, and have provided at least one evaluable pre-dose and post-dose PK blood sample. All PK analyses will be based on this analysis set.

8.1.2 Summary Statistics

In general, data will be summarized by means of summary statistics. All data collected in this trial will be documented with the help of subject data listings, summary tables, and figures. Data will be summarized with respect to population for analysis, sub-grouped by dose level of CyPep-1 and extension arms, regarding demographic and baseline characteristics, PK measurements, clinical efficacy observations and measurements, safety observations and measurements. Continuous variables will be summarised using descriptive statistics (arithmetic mean and/or geometric mean, standard deviation and/or coefficient of variation, median, minimum, and maximum). Categorical variables will be summarised using counts and percentages. All individual subject data will be listed.

